APPENDIX 1: SETTING UP MYCHART ACCOUNTS

All participants, regardless of whether or not they have a Jefferson PCP, will need to have a MyChart account. If they are randomized to the PREVENT group, they will need the account to have telehealth visits with their PCP. THE PARTICIPANT DOES NOT NEED TO HAVE AN EMAIL ADDRESS TO SET UP MYCHART.

Please ask the participant if they already have a MyChart account. If they do, ask them for their user name and password, and sign in using your computer to be sure that the account is active. If their user name or password is incorrect, work with them to re-set their account. You may need to call the help desk at [contact].

If they do not have an account, open the participant's snapshot on EPIC. Then click edit demographics>additional information>sign up. This will proxy you out of EPIC into the sign up website, where the participant will assigned a username and password.

APPENDIX 2: FACILIATING PCP TELEHEALTH VISITS

Web Browers: Please use Internet Explorer, Safari or Firefox.

Step 1: Activate Account from invite received through email or code at office check-out. SSN might be 9999, 1111 or 0000 depending if real SSN was NOT collected in office.

Step 2: Log in (if account active)

Step 3: Select Upcoming Visits

[figure not shown]
Step 4: Select Time/Date of Visit

Step 5: Begin Visit

Step 6: Complete both Extension and Plug-in

Step 7: Hardware Test

Step 8: You visit will now begin, please make sure your speaker volume are adjusted and that you have not muted your connection.

APPENDIX 3: GENERAL INSTRUCTIONS FOR ALL STAFF

- 1) To comply with HIPAA, all paperwork that contains PHI must be stored in a locked bank bag. You will be issued a HIPAA compliant bag that contains 2 keys. [name] and [name] will keep 1 key as a back-up. In addition, you will need to put your name and phone number on the outside of the bag. All cash for study incentives must be stored in the bag during transport.
- 2) Only use your Jefferson-issued devices for study-related purposes. Do not use any personal devices.
- 3) All communication regarding this study must be conducted through the Jefferson email system. For privacy purposes, Jefferson email accounts may not be forwarded to a personal smart phone or any other mobile device. PHI may only be included in an email if the recipient address is a Jefferson email.
- 4) All assessments and treatment sessions should be audio taped for quality assurance purposes. When participants are consented, they will be told that all visits will be audio taped. We will be giving you a digital recorder. Since the recordings are not encrypted, please do not ever say a participant's name or any other identifying information (e.g., birth date) on the tape. Please begin each recording with your name, the participant's study ID and initials, the date of the session, and the session type and number. For example, "This is [name]. I am with subject CABC123456 on 12/5/18 for a 6 month assessment". After the session is complete, please upload your tape onto the study shared drive. All files should be named with the participant's initials, ID, type of assessment, staff initials, and date. For example, "CABC123456 Baseline Part 2 RC 08-31-18." All tapes must be uploaded within 24 hours of the session being completed.
- 5) Schedules for the upcoming week must be sent on Fridays by noon.
- 6) We are required to report any potentially unsafe situations (e.g., suspected abuse, unsafe living situation, lack of heat/air conditioning, bug infestation) to the appropriate agencies. If you encounter a situation that needs reporting, please contact [name] at [contact] or [name] at [contact]. They will give you instructions for addressing the situation (e.g., contact Philadelphia Corporation for Aging). Within 24 hours of reporting the event via phone, please send an email to [name], [name], and [name] that describes the event, including any instructions given to you regarding the handling of the event.
- 7) This study requires home visits, and thus you may encounter potentially unsafe situations. If you encounter a situation that makes you feel unsafe (e.g., sexually inappropriate comments, gun in plain sight, bad neighborhood), or if you suspect that there is drug use or any other questionable activity going on in the home, you should leave immediately. You can politely say something like "I left some study materials in my car and I'm going to get them". And then just drive away. If you are in the home for an assessment, and the participant asks you for their incentive, you can give them the money, even if the assessment wasn't completed. You do not need to have them sign the receipt in this circumstance. Your safety is the top priority. Another strategy you can employ is to send a text (even a blank text) to [name], [name], or [name]. They will then call you right away to be sure that you are OK. Alternatively, you can ask [name], [name], or [name] to call you at a designated time when you are in a participant's home to check on you. If such an incident occurs, please email or call [name] or

[name] as soon as you can. [name] or [name] will call the participant and notify them that if they wish to continue participating in the study, all visits must occur at Jefferson. The study will cover the cost of the participant's roundtrip travel to Jefferson. Staff will no longer be permitted to make home visits to the participant.

8) If at any time you suspect that a participant is severely depressed, please email [name], [name], and [name] as soon as you can. If you think they are in a severe crisis, please follow the Psychiatric Emergency Plan that is described in the MOP. If the participant has suicidal ideation, please call [name] ASAP. Call [name] if you cannot reach [name].

APPENDIX 4: GENERAL INSTRUCTIONS FOR THE OUTCOME ASSESSOR

- 1) Please update the Contact Information Form at the 6 and 12 month assessments.
- 2) Unmasking:
 - Please ask the participant to NOT tell you what group they are in.
 - If the participant or any staff member discloses a participant's treatment assignment, please email [name] and [name] ASAP.
- 3) Missing data should be coded as follows:
 - Not Applicable = 9999
 - Refused = 7777
 - Missing due to impaired vision = 8888
 - Reason for missing data unknown 5555

4) Not Applicable (NA):

- NA is to only be used in 2 circumstances:
 - The question does not apply to the participant.
 - The participant is physically unable to respond to a cognitive question/task.
- Low literacy is not a reason for using NA. For example, if a participant is not able to read the
 words on the LAD, the response for each word should be "incorrect". Being wheelchair bound
 is also not a reason for using "NA" on questions regarding walking. These questions should be
 coded to reflect the fact that the participant is not able to do the activities.
- For the Diabetes Self Care Inventory, if a participant indicates that they never have low blood sugar, their response should be "never do it". This scenario also applies to question 6 (carry quick acting sugar for lows).
- For the questions on hypoglycemia, if the participant responds "No" to the first question (have you had a hypoglycemic episode), the response to the remainder of the questions in this section should be NA. Otherwise, all questions must have a response other than NA.
- 5) Part 2 of the baseline assessment:
 - Our goal is for all Part 2s to be completed within 2 weeks of Part 1.
 - This is very important to maintain participant interest in the study and to insure integrity of study data.

6) A1c results:

- Take a photo of the result with your Jefferson-issued iPhone and email to [name], [name], and [name].
- Please make sure the proper study ID is on the image.
- Enter the result in REDCap.

• [name] will verify the result entered in REDCap against the image.

7) Medication lists:

- At Part 1 of the baseline assessment, the ED staff will obtain a list of medications from EMR.
- At 6 and 12 months, staff will obtain medication lists from EMR.
- At the in-home assessments (Part 2 of baseline, 6, and 12 months), the Outcome Assessor will obtain self-reported medications.
 - First, ask to see the participant's medications bottles (or a list of they use a med box), including supplements and over the counter drugs.
 - Second, ask the participant's if they take any other medications that they aren't showing you.
 - Enter the medication names, doses, and number of time per day that they take each medication into REDCap.
- 8) Patient Health Questionnaire (PHQ 9):
 - If the participant seems severely depressed, please email [name], [name], and [name] as soon as you can. If you think they are in a severe crisis, please follow the Psychiatric Emergency Plan.
 - If the participant responds with anything other than "0" for question 9, please administer the Columbia-Suicide Severity Rating Scale.
 - If the participant has suicidal ideation, please call [name] ASAP. Call [name] if you cannot reach [name].
 - If the participant does not have suicidal ideation, please email a description of the participant's responses to the PHQ and the Columbia to [name], [name], and [name].
 - Be sure to include your impressions/observations of the participant.
- 9) After completing an in-home assessment, the Outcome Assessor should not leave the participant's home until they check REDCap to verify that:
 - (1) The correct participant ID was selected.
 - (2) All questionnaires are completed.
 - (3) Missing data are properly coded.

Once the Outcome Assessor gets back to the office, they will enter in REDCap all data that were collected on paper forms (e.g., LAD, MOCA). The Outcome Assessor should also check to be sure that all hard copies are properly labeled with the date of the assessment, the participant's initials and ID, and the assessment type (e.g., 6 months). Assessments should be marked as "unverified". The Outcome Assessor will then email [name], [name], and [name] to inform them that the assessment was completed. The subject line of the email should contain the participant's initials and ID (for example, CRJC0001). The body of the email should contain the following completed table (note example provided). The image of the A1c readout should be attached to the email. The email must be sent within 1 business day of the completion of the assessment.

Notification of Completed Assessment Table

Participant ID:	CRJC00001
Assessment date:	9/14/18
Assessment:	Part 2 Baseline
Comments:	

Once the email has been sent, the Outcome Assessor should upload the recording of the assessment to the designated location on the shared drive. All tapes must be uploaded and all hard copies of paperwork must be turned into [name] within 1 business day of the assessment. [name] will scan all hard copies and store them on the appropriate location of the shared drive. She will also download the A1c image and store it in the appropriate location on the shared drive.

10) To ensure that in-home baseline assessments are properly conducted, assessors will be notified of new subjects as follows:

A) In the email notification, the subject line will contain the participant ID and type of assessment (B1 and/or B2).

• B1: Consent, med release, pharm release, datasheet

• B2: A1C, vitals, MOCA, self-report questionnaires

Sometimes there were will be specific notes, which will be documented in the below table.

Subject Initials and ID: CXXX00002

Assess type: B1

Consented: Needs consent

Notes: Participant was discharged prior to consent, please consent

- B) Instead of having 2 separate folders for each assessment type, there will only be 1 participant folder. Anything that needs to be completed will all be put in the 1 folder. Each baseline packet will have an attached label on it. It will document where in the baseline process each participant is. You will be asked to check, initial and date each item as it is completed.
- For example, if the participant was consented in the ED, [name] will sign off on what was completed, and the Outcome Assessor will mark off when they complete Baseline Part 2.
- It is IMPERATIVE that the Outcome Assessor only use the folder that is assigned to each participant. Do NOT recycle folders or switch out for other participant.

Che	eck, initial and date wh	en completed:
	Consented:	
	Medical Release:	
	Pharmacy Release:	
	Data Sheet:	
	\$10 Payment:	
	A1C:	
	Baseline Part 2:	
	\$20 Payment:	

11) Please complete an Assessment Documentation Form in REDCap after each assessment to document the date, start time, end time, and travel time for each assessment.

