- 3. Test the efficacy of PREVENT to improve DM self-care over 12 months (secondary outcome). Hypothesis: PREVENT will increase Diabetes Self-Care Inventory scores to a greater extent than EUC over 12 months.
- 4. Determine if increasing subjective and/or objective indicators of access to care and/or DM self-care mediates PREVENT's reduction of DM-related ED visits and/or hospitalizations. Hypothesis: PREVENT will reduce DM-related ED visits and/or hospitalizations to the extent that it increases subjective and/or objective indicators of access to care and/or improves DM self-care.

The Exploratory Aims are to: 1) determine whether PREVENT reduces "all cause" ED visits/hospitalizations relative to EUC.; 2) determine whether Community Need Index scores, literacy, age, and/or sex moderate treatment effects; 3) determine if PREVENT improves glycemic control (i.e., lowers hemoglobin A1c levels), impacts DM-related health beliefs, reduces depression, and/or improves quality-of-life; 4) identify PREVENT's treatment features that confer its cultural relevance; and 5) estimate PREVENT's costs and net financial benefit to the healthcare system.

2: RESEARCH DESIGN SUMMARY

A. Study Purpose and Rationale: This Phase-III RCT will compare the efficacy of Community Care to Prevent Diabetes Emergencies (PREVENT) vs. Enhanced Usual Care (EUC) to reduce incident DM-related ED visits and/or hospitalizations over 12 months in 230 African Americans with diabetes (aged 40 and older), following an ED visit for a DM-related condition. Note that only 156 participants were randomized.

- B. Study Design: This study is a randomized controlled clinical trial in which the unit of randomization is the person. Participants will be randomized 1:1 to PREVENT (the experimental treatment) or EUC (the control condition).
- C. Sample: The sample will comprise 230 older persons (only 156 were randomized) who meet the following criteria:

Inclusion criteria:

- 1) African American race (self-identified)
- 2) Age ≥ 40 years
- 3) Type 1 or 2 DM
- 4) A recent ED visit

Exclusion criteria:

- 1) Diagnosis of dementia
- 2) Anti-dementia medication use
- 3) Life expectancy less than one year (in the opinion of the evaluating ED physician)
- 4) DSM-V psychiatric disorders other than anxiety or depression (as per EMR)
- 5) Intoxicated
- 6) Suicidal
- 7) In police custody or currently incarcerated

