Adjustable correlation to reference methods	
User-definable reference ranges available for HbA1c	
RS232, ASTM	
ASTM or POCT1-A2	
ASTM: Remote computer can be set up to lock out patient tests	
POCT1-A2: Remote computer can be set up to lock out patient	
tests, and send operator list to analyzer	
Standard USB 2.0	
Serial (9 pin)	
54 mm (2 in) width, thermal/label stock	
Supports standard PCL printer interface via USB port	

Diabetes Self-Care: The Diabetes Self-Care Inventory-Revised assesses self-reported adherence to 12 DM self-care behaviors (e.g., medications, glucose monitoring, exercise, diet). Total scores on this reliable and valid instrument correlate with HbA1c and are sensitive to treatment effects. We will test PREVENT's efficacy to improve DM self-care (secondary outcome), and also determine if change in DSCI-R score mediates PREVENT's treatment effects on ED/hospitalization rates (DM self-care as a mediator).

Depression: Clinically significant depressive symptoms occur in 25% of persons with DM. Depression impairs DM self-care and worsens glycemic control. We will assess depressive symptoms using the Patient Health Questionnaire-9 (PHQ-9), which has known reliability and validity in African Americans. The PHQ-9 yields a continuous measure of depressive symptoms based on their number, duration, and clinical significance. Depression is an exploratory outcome. For participants who respond with anything other than "Not at All" to the question on suicidal ideation, staff will administer the Columbia-Suicide Severity Rating Scale to assess risk for harm.

DM-Specific Quality-of-Life (QoL): We will use the Diabetes Quality of Life Brief Clinical Inventory to assess QoL. This 15-item scale yields a total health-related QoL score that predicts DM care behaviors and satisfaction with DM control. Diabetes quality of life will be an exploratory outcome.

Medical Comorbidity and Medication Use: We will use the Health-Related Quality of Life Comorbidity Index (H-RQLCI), which assesses 20 medical conditions (e.g., dyslipidemia, hypertension), and provides a valid index of overall medical comorbidity. The Outcome Assessor will review current health conditions and medications with participants, and the Research Assistant will obtain parallel information from medical records to ensure completeness and accuracy. We will use all sources of

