- Session 2: This session will begin with the telehealth visit with the PCP (about 20 minutes). The PCP will explain the collaboration with the CHW, and will assess the participant's current health status, answer questions about the recent ED visit, address relevant health beliefs, and review current medications (i.e., purpose, dosing, side effects). If the participant's most recent HbA1c is at target, the PCP reinforces the participant's current DM self-care strategies, and may consider a medication dose reduction. If the HbA1c level is not at target, the PCP will ask about treatment obstacles, and discuss ways to surmount them that are acceptable to the participant (e.g., diet modifications, medication change). After the telehealth visit, the CHW will review the PCP's recommendations with the participant. The CHW might say, "You've been taking metformin only when you thought your glucose was high. Dr. __ advises taking it daily to stay healthy. Let's talk about how metformin works and find a way to take it every day." They may then discuss how to integrate medication-taking into daily routines or a participant's personal values (e.g., trust in God). Taking medications might be linked to the message, "God has given us these medicines to live a

healthy life." At the end of session 2, the CHW and participant will schedule a telehealth visit with the DM nurse educator for session 3.

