Analysis: We will use structural equation modeling (SEM) to evaluate this aim, and will simultaneously model the DM-related ED visit/hospitalization count and each proposed mediator separately (i.e., PSQ-18 scores, number of received Diabetes Quality Metrics, and DSCI scores). The model will have paths from treatment to ED visit/hospitalization count (direct effect), treatment to mediator, and mediator to ED visit/hospitalization count. Using MPlus software, we will fit the SEM model and calculate the total indirect effect for the mediator. Mediation of the treatment effect on reduced incidence of DM-related ED visits and/or hospitalizations will be considered present if there is a significant path from treatment through the mediator to the primary outcome (i.e., an indirect effect). Standard errors will be calculated using bootstrapping. If there is evidence of mediation for more than one of the proposed mediators, we will fit a model that simultaneously considers the effect of the multiple mediators.

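### Scoring inventory items as never done when a participant has no low blood sugar makes the Diabetes Self-Care Inventory partly a measure of hypoglycemia (Secondary Aims 3 and 4)

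*Combined protocol and SAP*

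**What the plan says.** Appendix 4, item 4, limits Not Applicable to two circumstances, one of which is "The question does not apply to the participant". Within the same item it gives a special rule for the Diabetes Self-Care Inventory: "if a participant indicates that they never have low blood sugar, their response should be 'never do it". It then adds: "This scenario also applies to question 6 (carry quick acting sugar for lows". The next bullet concerns a separate set of hypoglycemia questions. There, a participant who answers No to the opening question is handled the other way: "the response to the remainder of the questions in this section should be NA".

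Section 6.2 describes the inventory as one that "assesses self-reported adherence to 12 DM self-care behaviors". The Introduction sets the direction of benefit: "PREVENT will increase Diabetes Self-Care Inventory scores to a greater extent than EUC over 12 months". Section 13.1.1 (Secondary Aims) uses the score twice:

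- as a continuous outcome in a mixed model, tested on change from baseline to 12 months (Aim 3);
- as one of three mediators in a structural equation model with a path from "mediator to ED visit/hospitalization count" (Aim 4).

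Section 13 gives no scoring rule for the inventory, no handling of Not Applicable items, and no sensitivity analysis that would undo the Appendix 4 coding.

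**The concern.** A participant who has no lows has no low to treat, yet is recorded as never doing the behavior. That is the same entry given to someone who has lows and ignores them. On question 6 the rule, as written, also overrides a participant who does carry sugar but has no lows. Part of the score then follows hypoglycemia status rather than self-care.

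Two analyses depend on it. In Aim 3, a participant whose lows stop loses points with unchanged self-care, and one who starts having lows and treats them gains points. In Aim 4, hypoglycemia sits on both sides of the path, because it moves the mediator score and hypoglycemia codes in Table 3 (section 6.2) also count toward the event outcome.

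**Working it through.** **No stated figure to reproduce.** The documents give no SD, effect size or power for the inventory. What follows checks the text and then illustrates size.

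**From the documents:** 12 items (6.2); at least 2 affected, namely the unnumbered low-blood-sugar item and question 6 (Appendix 4); higher score is better (Introduction); 78 randomized per arm (5.1).

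**Assumed, because the documents do not give them:** responses coded 1 to 5, equally weighted, with the never response equal to 1; mean *m* that an affected item would otherwise have, 2.5 to 5; score SD 6 to 10; share *p* reporting no lows, 0.3 to 0.7; arm difference *d* in that share at month 12, 0 to 0.2; a true effect of 0.5 SD; two-sided alpha 0.05; no dropout.

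**1. Share of the scale.** 2/12 = 16.7% of the items.

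**2. Effect on one participant.** The raw range is 12 × (5 − 1) = 48. The shift is s = 2 × (m − 1):

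- m = 2.5: s = 3, or 3/48 = 6.2%
- m = 3.5: s = 5, or 5/48 = 10.4%
- m = 5: s = 8, or 8/48 = 16.7% (both items fall from maximum to minimum)

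The ordering can reverse. Perfect self-care without lows gives 10×5 + 2×1 = 52, and (52 − 12)/48 = 83%. A participant with lows who scores 5 on the other ten items and 3 on these two gets 56, and (56 − 12)/48 = 92%.

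**3. Aim 3, arm contrast.** Write the recorded score as S − s·I, where I = 1 if the participant reports no lows. Change from baseline is then ΔS − s·ΔI. A participant whose status does not change carries a constant that cancels. With baseline balanced by randomization, the artificial contrast is −s·d, where d is the share in PREVENT minus the share in EUC:

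- d = 0: no bias
- d = 0.1: 5 × 0.1 = 0.5 points (0.3 to 0.8 over the range of m)
- d = 0.2: 5 × 0.2 = 1.0 point (0.6 to 1.6)

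The contrast moves against whichever arm has more participants free of lows. With no true effect and SD 8 (8.38 after the added variance in step 4), the standard error is 8.38 × √(2/78) = 1.34. The standardized shift is 0.5/1.34 = 0.37 or 1.0/1.34 = 0.75, and the rejection rate is 0.066 or 0.116 instead of 0.05.

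**4. Aim 3, noise when d = 0.** At one visit the variance becomes SD² + p(1 − p)s². With SD 8, p = 0.5 and s = 5 this is 64 + 0.25 × 25 = 70.25, so the SD is 8.38. Power = Φ(δ/(SD·√(2/78)) − 1.96). With δ = 4 it is 0.877 at SD 8 and 0.846 at SD 8.38. Over SD 6 to 10 and p 0.3 to 0.7, the power of 0.877 falls to between 0.822 and 0.861. If PREVENT also has more participants free of lows, power is 0.671 to 0.782 at d = 0.1 and 0.485 to 0.683 at d = 0.2. These figures compare month-12 scores. In the planned change-from-baseline test, the noise depends on how many participants switch status, which is not given.

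**5. Can d differ from zero, and in which direction?** Section 9.1 (Session 2) says that, when HbA1c is at target, the PCP in the PREVENT-only telehealth visit "may consider a medication dose reduction". That could mean fewer lows. Section 10.3.1 anticipates that better adherence may cause hypoglycemia, which would mean more lows. A difference is plausible, but its sign is not determined.

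**6. Aim 4.** The hypothesis needs a higher mediator score to go with fewer events. Under the coding rule, participants without lows receive a lower score and also do not incur the hypoglycemia events in Table 3. That association runs opposite to the hypothesized path and needs no arm imbalance. Its size depends on how much of the event count is hypoglycemia and on how common lows are. Neither is stated.

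**The case against.** The strongest reply is that the rule is the same for both arms and at every visit, and is applied by a masked assessor (8.2). Aim 3 tests change, so a stable participant's offset cancels and no bias follows from the rule alone. **This stands.** Bias in Aim 3 is conditional on a differential change in lows. A reader might infer that the contrast is biased against PREVENT, but sections 9.1 and 10.3.1 point in opposite directions, so the documents do not support that.

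Second, the sizes rest on an unprinted response scale, equal weights and a supposed arm difference. **This stands too.** Even that the never response is the lowest category is inferred from its wording and from higher scores being better.

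Third, Table 3 also counts skin infection, urinary infection, chest pain, renal failure, retinopathy, refills and any E08–E13 code, and the inventory is one of three mediators that are first modeled separately. This limits the likely effect on Aim 4 but does not remove it. The inference that the path is driven to zero or reversed goes further than the documents allow.

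Fourth, the bullet sits among other rules that restrict Not Applicable, such as those on low literacy and wheelchair use, and so looks deliberate. That does not make it coherent. The wheelchair rule records a real inability, whereas here there is no low to treat. The next bullet also codes the absence of an episode as Not Applicable.

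Fifth, carrying sugar is a precaution, so question 6 can be answered validly without lows. **This stands and shapes the remedy:** that item should be recorded as answered, not set to Not Applicable.

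**Conclusion.** The point holds at moderate severity, for one secondary outcome that is also a candidate mediator. Appendix 4 contradicts its own Not Applicable rule, and at least 2 of 12 items partly record hypoglycemia status.

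- **Aim 3:** added noise and some lost power. There is bias only if change in reported lows differs by arm, in a direction the documents leave open. On the assumed scale with m = 3.5, the bias would be 0.5 to 1.0 of 48 points for an arm difference of 10 to 20 percentage points.
- **Aim 4:** the rule works against the hypothesized mediator-to-event path, by an amount that cannot be determined from the documents.
- **Primary analysis:** not affected, because it does not use the inventory.

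The conflict in the text needs no assumption beyond reading the never response as the low end of the scale. Every numerical size is illustrative and rests on the assumptions listed in the working.

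**What to change.** 1. **Appendix 4, item 4.** Change the inventory bullet so that the low-blood-sugar item is coded Not Applicable (9999) when the participant never has lows, and question 6 is recorded as the participant answers it.
2. **Section 13.1.1 (Secondary Aims).** State that the inventory is scored as the mean of applicable items.
3. **Data already collected.** Repeat Aims 3 and 4 with a score that omits both items for all participants at all visits, and report it beside the as-collected 12-item score. Because the same ten items are then scored at every visit, this version also stays comparable if the instruction changes while visits are still due.
4. **Do not recode past visits from the hypoglycemia screen.** A reader may be drawn to this because the item is already collected. It asks about having had an episode, with no stated look-back period, whereas the rule is triggered by never having lows. Recoding from it could discard valid answers, especially on question 6.

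The cost is one reworded bullet, one scoring sentence, one extra analysis and a slightly shorter scale in that analysis. No new data are needed.
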